1. BACKGROUND E RAZIONALE

The diagnosis of Crohn's Disease (CD) is based on a combination of clinical, biochemical (serological and fecal), endoscopic, radiological, and histological investigations. In cases of suspected Crohn's disease, visualizing the small intestine plays a crucial role, as this area is affected in up to 83% of cases, with terminal ileal involvement in 90% of cases (1,2,3). In the absence of obstructive symptoms or known stenosis, European guidelines for inflammatory bowel diseases (ECCO guidelines) (3) and for digestive endoscopy (ESGE guidelines) (4) recommend to investigate the small intestine using Video Capsule Endoscopy (VCE). Clinical history and serum/fecal inflammatory markers are useful to select patients who may benefit from small bowel study (5,6). In particular, fecal calprotectin (FC) levels correlate with the endoscopic findings of VCE (7). An FC value of 100 µg/g appears to represent the best cutoff in terms of diagnostic accuracy (8), while an FC cutoff of 50 µg/g has the best negative predictive value of 91.8% (9). To perform VCE in symptomatic patients with increased FC may allow the diagnosis of CD in patients with negative ileocolonoscopy or with aspecific findings (10). Moreover, it lets safely exclude Crohn's disease thanks to a very high negative predictive value in the long term (11).

To reduce the reading time of VCE and increase the number of identified lesions during the examination, various artificial intelligence software/tools have been developed in recent decades. Recently, deep convolutional neural networks have demonstrated the ability to detect significant findings and reduce reading time without increasing the error rate (12,13). A CADe algorithm based on CNN, called SmartScan (OMOM, Chongqing Jinshan Science & Technology Group Co.), has been developed and evaluated for its ability to detect and classify lesions in the small intestine. In the validation phase, SmartScan-assisted reading (SSAR) achieved an overall higher detection rate and an overall higher sensitivity for all subtypes of findings compared to standard reading, with a mean reduction rate of the reading time of 89,3% (14). To date, no prospective study in clinical practice has evaluated the role of AI-assisted reading of VCE in suspected CD. This study aims to be the first prospective multicentric real-life trial to evaluate AI-assisted VCE using SmartScan in identifying typical mucosal abnormalities of the small intestine in patients with suspected CD and its ability to reduce reading time while maintaining the same diagnostic yield and diagnostic accuracy of standard reading.

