6. AIMS AND ENDPOINTS

6.1 Primary Endpoint

- Non-inferiority of AI-assisted reading (AIR) compared to standard reading (SR) in detecting (diagnostic yield - DY) typical lesions of suspected CD (erosions and/or ulcers and/or stenosis).

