6.2 Secondary Endpoint

- Overall diagnostic accuracy (sensitivity, specificity, PPV, NPV) of AIR and SR for detecting erosions and/or ulcers;
- Small bowel reading time of AIR and SR;
- Miss rate of AIR and SR for detecting erosions and/or ulcers;
- Correlation between VCE findings and clinical data.

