8. ANALYSIS AND STATISTICAL METHODS

8.1 Statistical Plan

Descriptive statistics will be provided in terms of mean \pm standard deviation (SD) or median and interquartile range interval (IQR) for the continuous variables; and in terms of frequency and percentage (%) or rate for the categorical variables. Group comparisons will be assessed by Student t-test or non-

parametric Mann-Whitney test for continuous variables and Chi-squared test or test for proportion for categorical variables.

The accuracy performances will be evaluated by assessing diagnostic yield (DY), accuracy, sensitivity, specificity, positive predictive value (PPV) and negative predictive value (NPV). Comparison of these metrics will be evaluated by test for proportions for independent samples or by McNemar test for paired samples. Analyses will be performed in both per-patient and per-lesion setting.

Further analyses to assess the predictors of diagnostic performance will involve the application of univariable and multivariable logistic regression models.

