8.2 Sample Size

Sample size calculation is assessed at per-patient analysis based on previous evidence by Xie et al 2022 (14) in which the detection rate of erosions and ulcers (common lesions in suspected Crohn disease) in AI-assisted reading was 11.5%, compared to 9% in standard reading (i.e. a difference of the two proportion around $D=2.5\%$). Considering a non-inferiority one side test for the difference between correlated proportions. with a non-inferiority margin $M= 0.02$, a type I error α of 0.05, a power $1-\beta$ of 80%, a difference of the two proportion $D=0.025$ and a plausible proportion of concordance on positive detection in both AIR and SR of 8%, the sample size needed to establish the non-inferiority of AI-reading with respect to Standard Reading is $N=164$ patients (i.e. 164 VCE). The size will be raised up to $N=180$ in order to take into account a potential dropout rate up to 10%. Details about the sample size computation can be found in Liu, J., et al. (19); and in PASS sample size software documentation at https://www.ncss.com/wp-content/themes/ncss/pdf/Procedures/PASS/Non-Inferiority_Tests_for_the_Difference_Between_Two_Correlated_Proportions.pdf).

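### Section 1 aims to show that AIR maintains the diagnostic accuracy of SR, but accuracy gets only tests of no difference and no margin, so a non-significant result cannot support that aim

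*Protocol*

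**What the plan says.** Section 1 closes with a statement of aim: to evaluate AI-assisted reading and "its ability to reduce reading time while maintaining the same diagnostic yield and diagnostic accuracy of standard reading". Two things are to be maintained, yield and accuracy.

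Section 6.1 gives a formal hypothesis to the first only: "Non-inferiority of AI-assisted reading (AIR) compared to standard reading (SR) in detecting (diagnostic yield - DY) typical lesions of suspected CD". The one margin in the Protocol, M = 0.02 in Section 8.2, is for the difference in detection proportions.

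Section 6.2 lists accuracy as a secondary endpoint with no hypothesis: "Overall diagnostic accuracy (sensitivity, specificity, PPV, NPV) of AIR and SR for detecting erosions and/or ulcers". Section 8.1 names how the accuracy metrics will be compared: "Comparison of these metrics will be evaluated by test for proportions for independent samples or by McNemar test for paired samples". It adds: "Analyses will be performed in both per-patient and per-lesion setting".

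Section 2, the formal objective, is more modest and speaks only of comparing the two readings.

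**The concern.** The aim is sameness; the named tests can only reject sameness. The one outcome compatible with the aim is p > 0.05, and that also arises when there are too few informative patients to see a difference. The fewer the positives, the easier that outcome is to obtain.

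At stake is the balance the study wants to report: a reading-time gain set against what, if anything, is lost in detection. Without a margin or an interval, a statement that accuracy was maintained would rest on absence of evidence.

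**Working it through.** **Inputs (Section 8.2).** Detection rates "in AI-assisted reading was 11.5%, compared to 9% in standard reading"; "a plausible proportion of concordance on positive detection in both AIR and SR of 8" per cent; M = 0.02; one-sided alpha 0.05; power 80%; N = 164.

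**1. The Protocol's own figure.** AIR-only = 0.115 - 0.08 = 0.035; SR-only = 0.09 - 0.08 = 0.010; D = 0.025. The restricted maximum-likelihood discordant proportions at the margin are 0.0197 and 0.0397. Then n = [(1.645 × √(0.0197 + 0.0397 - 0.0004) + 0.842 × √(0.045 - 0.000625)) / 0.045]² = 164.2. N = 164 reproduces, and it is sized for yield over all patients.

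**2. Patients who inform sensitivity.** Positive by either reading = 11.5 + 9 - 8 = 12.5%, so 0.125 × 164 = 20.5. This assumes that the cited rates carry over and that every lesion either reader sees is confirmed. At an assumed prevalence of 20% to 50% there would be 33 to 82 positives.

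**3. What those patients can exclude.** With no discordant pairs, the 95% score (Tango) interval for the paired difference is ±z²/(n + z²), with z² = 3.84.

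| Positives | Interval under perfect agreement |
|---|---|
| 20 | 3.84/23.84 = ±16 points |
| 33 | 3.84/36.84 = ±10 points |
| 82 | 3.84/85.84 = ±4.5 points |

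Any discordance widens these. With 20 positives, 4 found by SR only and 1 by AIR only, the exact McNemar p is 2 × (1 + 5)/32 = 0.375, while the score interval for AIR minus SR is -38 to +9 points.

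**4. How often McNemar misses a true loss with AIR.** Full enumeration, two-sided 0.05, counting rejections in the direction of AIR loss. The loss sizes are assumptions.

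| Positives | SR-only / AIR-only | Loss | Missed, exact | Missed, asymptotic |
|---|---|---|---|---|
| 20 | 25% / 5% | 20 points | 80% | 62% |
| 20 | 20% / 0% | 20 points | 80% | 41% |
| 20 | 15% / 5% | 10 points | 97% | 85% |
| 33 | 15% / 5% | 10 points | 88% | 77% |
| 82 | 15% / 5% | 10 points | 55% | 46% |

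**5. Does the yield test close the gap?** With no false positives, yield difference = 0.125 × sensitivity difference, so the 2-point margin equals 2/0.125 = 16 sensitivity points. The restricted-likelihood score test at N = 164 then passes AIR in 1.6% of trials for either 20-point loss and 8.9% for the 10-point loss at 20 positives.

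False positives count toward yield as read, but not toward sensitivity. As an illustration, take 12.5% as the share of true positives (no longer the share positive by either reading), with the 25%/5% pattern, and assume false positives in 4% (AIR only) and 1% (SR only) of the other 87.5%:

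- AIR-only = 0.125 × 0.05 + 0.875 × 0.04 = 0.04125
- SR-only = 0.125 × 0.25 + 0.875 × 0.01 = 0.0400
- yield difference = +0.00125, despite a 20-point sensitivity loss

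AIR then passes the yield test about 24% of the time.

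**The case against.** The strongest reply has four parts.

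*No such reading rule exists.* A reader might infer that the Protocol will treat a non-significant accuracy test as proof of equal accuracy. It nowhere says so. The phrase stands in the rationale, Section 2 speaks only of comparing, and accuracy is secondary. This stands: the risk is of misreading, not of a stated wrong rule. What remains is that Section 1 words the claim as an aim and Section 8.1 offers no other comparison by which to reach it.

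*This belongs in the SAP.* A secondary endpoint needs neither a margin nor its own sample size, and interval methods are commonly left to a SAP, which is not shown. Also right, so the absence of these is not the point. The point is a mismatch between an aim and a test that the Protocol itself states.

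*The primary endpoint already protects against lost sensitivity.* A reader might infer from the McNemar figures that a serious loss would usually slip through. If false positives are negligible, it would not: a 20-point loss nearly always fails the yield test. In the 4 versus 1 example, with all other patients concordant, the yield statistic is 0.12 against the 1.645 needed. The protection weakens once false positives enter, as step 5 of the working shows.

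*About 20 positives is not a design fact.* It is derived from a cited study's rates and applied to patients selected by the Table 1 criteria. The same rates imply sensitivities of 11.5/12.5 = 92% for AIR and 9/12.5 = 72% for SR, so a loss with AIR is an assumption and not a Protocol figure. The count also does not limit specificity, overall accuracy or the per-lesion analysis. All of this stands.

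**Conclusion.** The concern holds in a limited form. The Protocol sets an aim of maintained accuracy, gives accuracy only tests of no difference, and reserves its single margin for yield. A non-significant accuracy comparison cannot support that aim.

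The size depends on the number of confirmed positives: about ±16 points at best with 20, and about ±4.5 at best with 82. The first figure rests on the Section 8.2 rates with every positive confirmed; the second rests on an assumed 50% prevalence.

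The documents do not support saying that equal accuracy will be declared from p > 0.05, that the study will have only 20 positives, or that the yield test gives no protection. The point concerns a secondary endpoint and leaves the primary hypothesis and N = 164 untouched. It should still be corrected, because the better method is simple and the present wording invites a claim that the comparison cannot carry.

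**What to change.** In Section 8.1, state that sensitivity, specificity and accuracy of AIR and SR are reported per patient as paired differences with 95% score (Tango-type) confidence intervals, and that a non-significant McNemar or proportion test is not evidence of maintained accuracy.

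In Section 1, limit the word maintaining to diagnostic yield and describe the accuracy comparison as estimation. If the investigators want to keep the accuracy claim, they should fix a margin before the data are seen and require the lower confidence limit to lie above minus that margin.

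The expected number of positives need not be written into the Protocol, since it is an assumption.

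The cost is a few sentences in the Protocol or SAP and a routine interval, with no extra patients or readings. The downside is that the study gives up a claim of maintained accuracy unless the interval supports it.

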2. STUDY OBJECTIVE

The objective of the study is to evaluate the role of AI-assisted VCE using the OMOM SmartScan in detecting typical small bowel inflammatory lesions (i.e. erosions and ulcers) in patients with suspected CD, and comparing AI with standard reading.

3. STUDY DESIGN

This is an observational, prospective, multicentre study with repeated assessment of VCE (performed according to the standard of care, with a subsequent second reading AI-assisted for research purposes with no commercial intent).

The expected duration of the study is 36 months, with a proposed start date of 01/03/2025. A maximum enrolment period of 24 months is anticipated.

Details on the study design are discussed in the sections below.

4. STUDY POPULATION

Eligible patients for the study are those with clinical symptoms and laboratory results suggestive of CD who have previously undergone an ileocolonoscopy which excluded other organic pathology and/or resulted inconclusive for CD (aspecific terminal ileitis).

5. INCLUSION AND EXCLUSION CRITERIA

5.1 Inclusion criteria

- Age ≥ 18 and ≤ 75 years
- Clinical suspicion of Crohn's Disease (CD) with/without occlusive symptoms (see Table 1 below)
- Ileocolonoscopy: negative examination, aspecific inflammatory findings
- Signed informed consent form.

5.2 Exclusion criteria

- Known diagnosis of CD
- Endoscopic diagnosis of active diverticular disease, colorectal cancer, ulcerative colitis, or infectious colitis
- Positive stool tests for pathogenic bacteria, parasites, and *C. difficile* infection within 3 months before CE
- Known intestinal obstruction or unconfirmed small bowel patency
- Use of NSAIDs in the 4 weeks before ileocolonoscopy and before VCE
- Known gastrointestinal motility disorder
- Known or suspected delayed gastric emptying
- Swallowing disorders
- Allergy or other contraindications or intolerance to the medications/devices used in the study
- Endoscopic placement of the capsule
- Any condition that prevents adherence to the study
- Pregnancy
- Participation in another clinical trial involving experimental drugs or devices
- Concomitant life-threatening condition
- Chronic kidney disease
- Inability to sign the informed consent

6. AIMS AND ENDPOINTS

6.1 Primary Endpoint

- Non-inferiority of AI-assisted reading (AIR) compared to standard reading (SR) in detecting (diagnostic yield - DY) typical lesions of suspected CD (erosions and/or ulcers and/or stenosis).

6.2 Secondary Endpoint

- Overall diagnostic accuracy (sensitivity, specificity, PPV, NPV) of AIR and SR for detecting erosions and/or ulcers;
- Small bowel reading time of AIR and SR;
- Miss rate of AIR and SR for detecting erosions and/or ulcers;
- Correlation between VCE findings and clinical data.

7. METHODOLOGY AND OPERATIVE PROCEDURES

Screening

Patients with signs and symptoms of suspected CD AND negative/inconclusive ileocolonoscopy will be enrolled. Inconclusive ileocolonoscopy will be defined as the presence of aspecific inflammatory mucosal alterations in the ileum or colon, that do not allow a final diagnosis of CD.

At the Screening Visit, active or recent gastrointestinal infection will be ruled out. Patients who will present with sub-occlusive symptoms will undergo a patency capsule to exclude the presence of a stenosis. Only patients with a prompt patency transit (expulsion within 30-33 hours of the intact patency capsule or its absence on abdominal X-ray) will be enrolled.

Signs and symptoms of suspected CD will be defined according to the ECCO Guidelines and ICCE criteria. An ad-hoc protocol defined by the authors will be applied to define the patient with suspicion of CD, stratifying all factors as major or minor criteria (see **Table 1**): the presence of at least two major criteria or the combination of one major criteria with three minor criteria will be necessary for patient enrolment.

CE protocol

SBCE will be performed using the OMOM Capsule System (Chongqing Jinshan Science & Technology (Group) Co), equipped with a DNN based system called SmartScan (SC), which is able to automatically select suspected lesions thus creating a very short video constituted only by selected images.

The SC100 system tested in this study consists of:

1. **Ingestible microcamera SC1 OMOM HD:** the capsule is 25.4 x 11.4 mm in size, with a weight of 3.0 grams. It is embedded with a single camera with a 172° field of view; sampling rate varies between 4 and 35 frames per second, and the image resolution is 512 x 512 pixels. The depth of field is optimized between 0 and 50 mm. The Truecolor 24-bit model allows for high colour depth, displaying up to 16 million colours per pixel.
2. **Recorder and SC-RD1 belt:** antennas receive data from the OMOM video capsule
3. **Vue Smart Work Station:** SmartView reading software equipped with the CNN model. The CNN model analyses raw data during the download phase from the recorder and during video review. It supports the operator in reviewing and reporting through three functionalities:
 - **SmartScan:** Based on an AI algorithm developed and validated for reviewing capsule videos of the stomach and small intestine, it eliminates redundant images and identifies 16 different types of abnormalities found in the images.
 - **SmartView:** Allows the operator to quickly "navigate" through the entire video, showing only the images selected by SmartScan and highlighting the selected video portions on the timeline that can be viewed separately from the rest of the footage.
 - **SmartFinding:** Displays only the images selected by the operator, providing a description and characterization of the detected abnormalities.

VCE will be performed at each centre according to local regulations and requirements, and the study protocol will address the bowel preparation regimen as well as the reading methods and post-procedural analysis for each patient.

Pre-Procedural Patient Management

To achieve homogeneous results, a standard bowel preparation regimen will be adopted, involving the intake of Polyethylene glycol (PEG) in a split-dose manner, as recommended by ESGE guidelines (16).

The regimen includes:

- The day before VCE: the patient may have breakfast and consume a light meal until 3 PM, followed by fasting. At 7:00 PM, take dose 1 of the bowel preparation with a very low volume PEG solution (PlenVu, Norgine).

- The day of VCE: take dose 2 in the morning of the procedure so that it is completed 2 hours before capsule ingestion, fasting from liquids for 2 hours after ingestion, and fasting from solids for 4 hours after capsule ingestion. After this, the patient is allowed to drink clear liquids and have a light meal.

Post-Procedural Management

Patient follow-up will occur according to routine clinical practice, collecting any cases of retention or adverse events. Patients undergoing VCE will be instructed to check for the expulsion of the capsule and to report any relevant symptom that may suggest potential capsule retention. Patients who do not notice the expulsion of the capsule within 2 weeks of ingestion will undergo an abdominal X-ray to exclude capsule retention. Clinical and laboratory data of all patients enrolled will be collected at follow-up visits (at 6 and 12 months).

Video Capsule Reading

At the site of patient's enrolment, investigators will perform VCE by evaluating the video in standard mode according to the recommendations of the European Society of Gastrointestinal Endoscopy, at 10 frames per second in the small intestine, and 20 frames per second in the esophagus, stomach, and colon. Reference points (first gastric image, first duodenal image, first cecal image) will be manually selected by the reader. The cleanliness level will be assessed as adequate (excellent/good) or inadequate (fair/poor) according to the qualitative scale of Brotz. Inflammatory lesions will be described using the Nomenclature and semantic descriptions defined by Leenhardt et al. in the International Delphi consensus (17), specifically modified for this study to ensure inter-observer agreement in the description of lesions (see **Figure 1**). Lesions will be reported specifying their time of appearance (h: min: s, timing of single frames). In case of multiple inflammatory lesions (>5 per tertile), time of appearance won't be specified and the reader will quantify the pathology burden for every tertile reported as 5-10 or >10 inflammatory lesions, specifying the predominant type of inflammatory lesion). At the end of the reading, readers will also calculate the Lewis score for each video. The Lewis score, used to score the known Crohn disease, split up the small bowel in three tertiles based on transit time, evaluating separately for each tertile the presence of villous edema, ulcerations, and stenosis. The assessment of these parameters is based on number, longitudinal extent and specific characteristics. The final score is the highest value among the

three tertiles (see **Figure 2** for details). A score between ≥ 135 and < 790 indicates mild inflammation; and a score of ≥ 790 signifies moderate-to-severe inflammation (18).

Investigators at the enrolment centre will anonymize the video which will be randomly reallocated to another centre for the second blind reading assisted by AI (i.e., the readers performing the capsule reading in AI mode will not be aware of the results of the first reading in standard mode). The same instructions specified earlier will be applied to the AI-assisted reading, except for the reading speed, limited to 2-5 frames per second.

To note, the first reading will always be performed at the centre where the patient is enrolled (not randomized). This choice is made to ensure that patients receive the standard level of care at the centre and have full access to clinical history and medical documents for the physician who ultimately diagnoses the condition.

Comparison and Shared Review

An external researcher will compare the results of standard and AI-assisted readings from all the centres to assess the agreement of the observations reported by both readers. For videos containing less than 5 inflammatory lesions per tertile, the correspondence of reading will be evaluated comparing the type and the timing of the lesions. For videos with diffuse disease and multiple lesions, the correspondence of readings will be evaluated considering the number of lesions category (5-10 or >10 , classified for predominant type) reported in a specific tertile. In case of disagreement (for example, lesions missed by either reader in AIR or SR), an external expert reader (read more than 500 capsules) will review the discordant footage, blind to the source of the videos, open exclusively to the footage being reevaluated.

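### Each reader sets the duodenal and caecal landmarks separately, yet readings with multiple lesions are matched by tertile without time stamps, so a landmark difference can look like an AIR/SR disagreement

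*Protocol*

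**What the plan says.** Protocol section 7, Video Capsule Reading, sets out the SR task first. The small bowel is read "at 10 frames per second in the small intestine, and 20 frames per second in the esophagus, stomach, and colon". On landmarks it says: "Reference points (first gastric image, first duodenal image, first cecal image) will be manually selected by the reader". Each lesion is reported with its time of appearance, except that in a tertile with more than five inflammatory lesions the reader gives no times, only a category (5-10 or >10) and the predominant type. The scoring instruction is "At the end of the reading, readers will also calculate the Lewis score for each video", and the Lewis score is described as one that "split up the small bowel in three tertiles based on transit time, evaluating separately for each tertile the presence of villous edema, ulcerations, and stenosis".

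Once anonymised, the video goes to another centre for a blind AIR reading, under this rule: "The same instructions specified earlier will be applied to the AI-assisted reading, except for the reading speed, limited to 2-5 frames per second". Speed is the only stated exception, so landmarking carries over. Nothing in the section says that the first reader's landmarks travel with the video.

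Section 7, Comparison and Shared Review, has an external researcher compare the two readings. Sparse lesions are matched on type and timing. Multiple lesions are matched on the count category within a given tertile. Disagreements go to an external expert who is blind to the source. Section 6.2 lists the miss rate of each reading and "Small bowel reading time of AIR and SR" as secondary endpoints, and section 8.1 plans per-lesion as well as per-patient analyses.

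**The concern.** A tertile is a third of the interval between one reader's duodenal mark and the same reader's caecal mark. If the marks differ, the first, second and third tertiles of SR and AIR are different stretches of bowel. The comparison still treats them as the same segments.

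This would do little harm if every lesion had a time, because the recording is common to both readings and lesions could be matched directly. The time is dropped exactly where matching relies on the tertile. A difference in landmarks can then be counted as a disagreement in detection, or as a miss by one reading, and the data needed to separate the two do not exist. Section 1 cites terminal ileal involvement in 90% of cases, so lesions close to the caecal mark are to be expected.

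**Working it through.** **1. The plan's own figure.** Section 8.2 gives N=164 from detection rates of 11.5% (AIR) and 9% (SR), 8% positive on both, margin 0.02, one-sided α 0.05 and power 80%.
- Discordant cells: 0.115 − 0.08 = 0.035 and 0.09 − 0.08 = 0.010.
- Variance under the alternative: 0.045 − 0.025² = 0.044375.
- Variance under the null (restricted maximum likelihood, q = 0.03968): 2q − 0.02 − 0.02² = 0.05896.
- N = [(1.6449·√0.05896 + 0.8416·√0.044375)/0.045]² = 164.2.

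This reproduces the plan's 164. No input involves a landmark, a tertile or a reading time, so the point leaves N unchanged.

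**2. How far tertile boundaries move.** With duodenal mark S and caecal mark E, the boundaries lie at S + (E − S)/3 and S + 2(E − S)/3. If only E differs between readers by d minutes, they move by d/3 and 2d/3. If only S differs, they move by 2d/3 and d/3. The documents give no figure for d, so the values below are assumptions.

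| Difference d at the caecal mark | First boundary moves | Second boundary moves |
|---|---|---|
| 5 min | 1.7 min | 3.3 min |
| 10 min | 3.3 min | 6.7 min |
| 20 min | 6.7 min | 13.3 min |

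**3. What that does to a category.** Assume a transit of 4 h (240 min) on the SR marks, the same duodenal mark for both readers, and an AIR caecal mark 10 min later.
- SR tertiles (min): 0–80, 80–160, 160–240.
- AIR tertiles (min): 0–83.3, 83.3–166.7, 166.7–250.
- A lesion between 160 and 166.7 min is in the third tertile for SR and the second for AIR.

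Suppose SR counts 11 lesions in its last tertile, one of them in that strip, with none between 240 and 250 min. AIR, detecting every one of them, counts 10. SR reports >10 and AIR reports 5-10. If 11 lesions were spread evenly over 80 min, the expected number in the strip would be 11 × 6.67/80 = 0.92, so the example is not contrived. At the lower end, six lesions with two in the strip become four. SR then reports an untimed category and AIR a list of timed lesions, and no matching rule covers that pair.

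**4. Where realignment is possible.** Sparse lesions carry a time and can be matched whatever the tertile boundaries. Lesions in a tertile with more than five carry none, so no later analysis can recount them on a common window.

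**5. Reading time.** If small-bowel time is taken between each reader's own marks, the two readings are timed over different windows. At 4 frames per second, the lowest stated sampling rate, 10 min of transit is 10 × 60 × 4 = 2,400 frames, or 2,400/10 = 240 s = 4 min of SR at 10 fps. A 4 h window is 57,600 frames, or 96 min, so the difference is 4/96 = 4.2% of SR time. For AIR it depends on how many selected images fall in the extra stretch.

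**6. Primary yield.** Moving an internal boundary cannot turn a patient with a lesion into one without. Only an outer mark could, and only if the patient's sole lesion lay between the two readers' marks.

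**The case against.** Several points on the other side stand. Sparse lesions are matched on time, so tertiles matter only in diffuse disease. Disagreements go to a blinded expert. Independent landmarking is a natural part of a blinded second reading and of real-life practice. The exact content of a timer is often left to an SAP or reader manual. These points limit the problem but do not remove it: for an untimed tertile the expert has no common definition of the footage to review, and landmarks reveal no lesion result, so sharing them does not unblind anyone.

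A reader might infer more: that AIR must replay the whole small bowel at 2-5 fps, taking 10/5 = 2 to 10/2 = 5 times as long as SR, and that the AI clip cannot serve the tasks AIR inherits. The documents do not support this. Section 7 never requires a full replay. It describes software able to "automatically select suspected lesions thus creating a very short video constituted only by selected images", and says SmartView displays only the selected images while the entire video stays navigable, so landmarks and Lewis extent can be taken from the full footage. At 2-5 fps AIR playback is still faster than SR if fewer than 2/10 = 20% to 5/10 = 50% of frames are kept.

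Nor do the extra tasks undo the time saving. Take 96 min for SR and apply the cited 89.3% reduction, which gives 96 × 0.107 = 10.3 min. An assumed 10 min for landmarks, cleanliness and Lewis scoring, charged to both modes because both have these tasks, gives (10.3 + 10)/(96 + 10) = 19%, still a reduction of about 81%.

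**Conclusion.** The point holds for landmarks and tertile matching. The protocol has each reader set the small-bowel window, compares multiple-lesion readings by tertile, and discards the times that would allow realignment. A 10-minute difference at one end mark moves the boundaries by 3.3 and 6.7 min; assumed differences of 5 to 20 min give 1.7 to 13.3 min. That is enough to change a count category with identical detection. How often it would happen cannot be derived from the documents, which give neither the landmark disagreement between readers nor the share of patients with diffuse disease.

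The consequences fall on per-lesion agreement, miss rate and, modestly, small-bowel reading time. N=164 is unaffected and the per-patient primary yield is unlikely to change. The conclusion rests on the literal reading that landmarking is among the instructions carried over to AIR and that no marks are sent with the video. Which footage AIR covers deserves a clarifying phrase; it is not evidence that the reading-time comparison would reverse.

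**What to change.** Amend section 7, Video Capsule Reading, so that the first duodenal and first caecal images are set once per video at the enrolling centre, sent with the anonymised recording, and used as the common window and tertile boundaries for both readings. Make the Comparison and Shared Review text refer to the same boundaries. This has to be in place before the second readings, because untimed counts cannot be reassigned afterwards.

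In the same edit, state that the lesion search in AIR uses the SmartScan-selected images, and that small-bowel reading time counts the same tasks in both modes.

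The cost is protocol wording and one reader instruction, and the second reader has one task fewer. The small downside is that AIR no longer tests landmark finding, which is not an endpoint. Blinding is kept, since the marks say nothing about lesions.
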